4.1. Protocol Deviations

Important protocol deviations (including deviations related to the study inclusion/exclusion criteria, conduct of the trial, patient management or patient assessment) will be summarized and listed.

Important deviations which resulted in exclusion from the analysis population will also be summarised and listed. (Please refer to [Appendix 1: Protocol Deviation Management and Definitions for Per Protocol Population](#)).

Protocol deviations will be tracked by the study team throughout the conduct of the study in accordance with the Protocol Deviation Management Plan.

- Data will be reviewed prior to freezing the database to ensure all important deviations and deviations which may lead to exclusion from the analysis are captured and categorised on the protocol deviations dataset.
- This dataset will be the basis for the summaries and listings of protocol deviations.

A separate summary and listing of all inclusion/exclusion criteria deviations will also be provided. This summary will be based on data as recorded on the inclusion/exclusion page of the eCRF.

5. CONSIDERATIONS FOR DATA ANALYSES AND DATA HANDLING CONVENTIONS

5.1. Study Treatment & Sub-group Display Descriptors

Treatment Group Descriptions			
RandAll NG		Data Displays for Reporting	
Code	Description	Description	Order in TLF
D1	GSK1278863	Daprodustat	1
D2	Epoetin beta pegol	Epoetin beta pegol	2

Treatment comparisons will be displayed as follows using the descriptors as specified:

1. Daprodustat vs Epoetin Beta Pegol

5.3. Multicentre Studies

It is anticipated that subject accrual will be spread thinly across centers and summaries of data by center would be unlikely to be informative. Therefore, data from all participating centers will be pooled for analysis.

5.4. Examination of Covariates, Other Strata and Subgroups

5.4.1. Covariates and Other Strata

The list of covariates and other strata will be used in statistical analyses, the strata will also be used for subgroup analyses.

Randomization is stratified by prior ESA use and baseline Hgb in Cohort 1 and Cohort 3 (ND subjects). Baseline Hgb will be included as a covariate in the primary efficacy analyses. Prior ESA use and baseline Hgb will be included as covariates in the principal secondary efficacy analyses. The reasons why prior ESA use will not be included in the primary analyses are 1) the data for the primary endpoint is longitudinal data and the visit effect and the interaction with visit are important. 2) if including prior ESA use in the analyses the model will be complicate and it will be difficult to interpret the results. While, the data for the principal secondary endpoint is not longitudinal data and it has no visit data. Thus, it will not be complicate even if including prior ESA use in the model.

Category	Details
Strata	ESA use, Baseline Hgb
Covariates	
For primary efficacy analyses:
 
 Mixed model for repeated measurements (MMRM) including covariates of treatment group, baseline Hgb, visit, treatment-by-visit interaction, and baseline Hgb-by-visit interaction will be used. 
For principal secondary efficacy analyses:
 
 Logistic regression model including treatment group, baseline Hgb, and current ESA therapy (presence or absence) as covariates will be used.

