2. SUMMARY OF KEY PROTOCOL INFORMATION

2.1. Changes to the Protocol Defined Statistical Analysis Plan

Changes from the originally planned statistical analysis specified in the protocol amendment 04 (Dated: 03/JUL/2017) are outlined in [Table 1](#).

Table 1 Changes to Protocol Defined Analysis Plan

Protocol	Reporting & Analysis Plan	
Statistical Analysis Plan	Statistical Analysis Plan	Rationale for Changes
9.3.3 Adjustment for Multiplicity Adjustment for multiplicity will be applied to maintain an overall type I error rate of 5%. After a preliminary assessment, the primary endpoint will be evaluated to demonstrate the non-inferiority at a one-sided significance level of 2.5% (i.e. two-sided significance level of 5%).	5.5 Multiple Comparisons and Multiplicity Adjustment for multiplicity will be applied to maintain an overall type I error rate of 2.5% (one-sided) . After a preliminary assessment, the primary endpoint will be evaluated to demonstrate the non-inferiority at a one-sided significance level of 2.5%.	An overall type I error rate (α) of 2.5% is a one-sided nature of the non-inferiority test, which is the primary analysis for this study. This can be applicable to the following superiority test to maintain $\alpha=2.5\%$. Practically, this is equivalent to two-sided significance level of 5%.
9.4.1 Primary Efficacy Analysis Analysis of covariance (ANCOVA) will be conducted as sensitivity analysis to MMRM. This model includes treatment group and baseline Hgb.	7.1.6 Sensitivity and Supportive Analyses Analysis of covariance (ANCOVA); it will be conducted as supplementary analysis to MMRM. This model includes treatment group, baseline Hgb, and prior ESA use .	Prior ESA use is considered as important factor impacting Hgb.

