5.4.2. Examination of Subgroups

The list of subgroups may be used in descriptive summaries and statistical analyses.

Subgroup	Categories
Prior ESA Use ^[1]	Non-user, User
Baseline Hgb (g/dL) ^{[1][2]}	ESA non-users: <=9.5, >9.5 ESA users: <11.0, >=11.0
Age (year)	< 65, >=65
Sex	Female, Male
Prior ESA Dose (IU/week)	<4,500, >=4,500 ^{[3][4]}
Prior ESA Type	Epoetin, Epoetin beta pegol, Darbepoetin alfa
ERI ^[3]	< median, >= median
Baseline Iron Use ^[5]	Yes, No

Subgroup	Categories
Baseline Weight (kg)	< 55, >=55
Baseline BMI (kg/m ²)	<20, >=20
History of Diabetes ^[6]	Yes, No
Dialysis ^[7]	ND subjects, PD subjects
CKD Stage ^[8]	Stage 3 (30=<eGFR<60), Stage 4 (15=<eGFR<30), Stage 5 (eGFR<15)

NOTES:

- BMI = Body Mass Index
 - See Section 15.6.1 for the subgroup derivations
- [1] Stratum code will be used to determine category. Stratum code=1: ESA non-user, Baseline Hgb <= 9.5, 2: ESA non-user, Baseline Hgb > 9.5, 3: ESA user, Baseline Hgb < 11.0, 4: ESA user, Baseline Hgb >= 11.0.
- [2] Hemocue Hgb at Day 1 will be used for categorization.
- [3] Additional thresholds might be added in order to divide the population equally as appropriate.
- [4] Standardized dose on epoetin i.v. (IU/week) will be used for subgroup.
- [5] Subjects who used ferric citrate (trade name: Riona) will also be included in Baseline Iron Use group. This category will be used just for iron analyses. See Section 15.6.3.
- [6] Past or current history of diabetes
- [7] This subgroup will be used for study population analyses and safety analyses.
- [8] CKD Stage will be determined by eGFR (mL/min/1.73m²) at a screening visit

For prior ESA use, the subgroup of non-users in PD subjects is small. Therefore endpoints summarized for PD subjects (i.e. Safety or Efficacy PD population) by prior ESA use will also be listed for the ESA non-users in PD subjects.

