7.1.5.1. Statistical Methodology Specification

Endpoint / Variables

 • Mean Hgb during the primary efficacy evaluation period (Weeks 40 to 52)
Model Specification

 • Analyses will be conducted by MMRM as follows: $Hgb_{ik} = \beta_0 + \beta_{baseline} * Baseline_i + \beta_j + \beta_k + \beta_{jk} + \beta_{baseline*k} * Baseline_i + \epsilon_{ik}$ 
Hgb_{i, week}: Hgb measurement for subject i at visit k β_0: Intercept $\beta_{baseline}$: baseline Hgb effect Baseline_i: Hgb measurement for subject i β_j: treatment effect (j= daprodustat, epoetin beta pegol) β_k: visit effect (k = Week 4, Week 8, ..., Week 52) β_{jk}: treatment-by-visit interaction $\beta_{baseline*k}$: baseline-by-visit interaction ϵ_{ik}: random error for subject i at visit k i: subject (i = 1, 2, ..., N) N: number of subjects included in the analysis
 • The model parameters will be estimated using Restricted Maximum Likelihood (method=REML) with the Newton-Raphson algorithm. • The Kenward-Roger method for calculating the denominator degree of freedom will be used. • The variance-covariance structures for repeated measures within the individual subject will be unstructured (type=UN). • LS means for treatment j at visit k will be calculated as follows. $\mu_{jk} = \beta_0 + \beta_{baseline} * \mu_{baseline} + \beta_j + \beta_k + \beta_{jk} + \beta_{baseline*k} * \mu_{baseline}$ 
μ_{jk}: LS mean for treatment j at visit k $\mu_{baseline}$: mean for baseline Hgb
 • Model based mean Hgb during the primary efficacy evaluation period for treatment j will be calculated as follows $\begin{aligned} \mu_j^{*evaluation} &= (\mu_j^{*Week\ 40} + \mu_j^{*Week\ 44} + \mu_j^{*Week\ 48} + \mu_j^{*Week\ 52})/4 \\ &= \beta_0 + \beta_{baseline} * \mu_{baseline} + \beta_j + (\beta_{Week\ 40} + \beta_{Week\ 44} + \beta_{Week\ 48} + \beta_{Week\ 52})/4 + (\beta_j^{*Week\ 40} + \beta_j^{*Week\ 44} + \beta_j^{*Week\ 48} + \beta_j^{*Week\ 52})/4 + (\beta_{baseline*Week\ 40} + \beta_{baseline*Week\ 44} + \beta_{baseline*Week\ 48} + \beta_{baseline*Week\ 52}) * \mu_{baseline}/4 \end{aligned}$ • The treatment difference for model based mean Hgb during the primary efficacy evaluation period will be calculated as follows $\begin{aligned} \mu_{daprodustat}^{*evaluation} - \mu_{epoetin}^{*evaluation} &= \beta_{daprodustat} - \beta_{epoetin} + (\beta_{daprodustat*Week\ 40} + \beta_{daprodustat*Week\ 44} + \beta_{daprodustat*Week\ 48} + \beta_{daprodustat*Week\ 52})/4 - (\beta_{epoetin*Week\ 40} + \beta_{epoetin*Week\ 44} + \beta_{epoetin*Week\ 48} + \beta_{epoetin*Week\ 52})/4 \end{aligned}$ • P-value for non-inferiority test will be based on the following t test statistic (Mascha 2011):

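### The primary MMRM leaves out prior ESA use, a randomization stratum, for a reason that does not hold; the cost is a mildly conservative test and a missing-data assumption not conditioned on that factor

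*SAP*

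**What the plan says.** Section 5.4.1 describes the design: "Randomization is stratified by prior ESA use and baseline Hgb in Cohort 1 and Cohort 3 (ND subjects". For the primary endpoint it then specifies: "Mixed model for repeated measurements (MMRM) including covariates of treatment group, baseline Hgb, visit, treatment-by-visit interaction, and baseline Hgb-by-visit interaction will be used". Section 7.1.5.1 writes out the same model, with a "visit effect (k = Week 4, Week 8, ..., Week 52" and an unstructured covariance matrix. Prior ESA use is in neither place.

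Section 5.4.1 gives two reasons for this. The first is that "the data for the primary endpoint is longitudinal data and the visit effect and the interaction with visit are important". The second is that "if including prior ESA use in the analyses the model will be complicate and it will be difficult to interpret the results".

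Elsewhere the SAP treats the factor differently. Table 1 in Section 2.1 adds it to the supplementary ANCOVA because "Prior ESA use is considered as important factor impacting Hgb". The logistic model for the principal secondary endpoint (Section 7.2.5.1) includes it too.

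**The concern.** An analysis normally carries the factors that the randomization balanced on. When a prognostic stratum is left out, its variance stays in the residual although the design has already balanced it between arms. The reported standard error is then larger than the true sampling error, and the interval is wider than it needs to be.

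Missing data are a second matter. Section 7.1.4 handles withdrawal under missing at random. The primary model makes that assumption conditional on treatment, baseline Hgb and observed post-baseline Hgb, but not on ESA use. Users and non-users enter under different regimens (Section 2.3), and a given baseline Hgb has been reached on treatment in one group and without it in the other. The model nevertheless fits one baseline slope per visit to both.

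No planned analysis supplies an overall ESA-adjusted treatment difference in the ITT population, where non-inferiority is judged. The ANCOVA runs only on mITT and PP and drops subjects who withdraw before Week 40 (Section 7.1.6.2). The ITT subgroup MMRMs give two separate differences.

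**Working it through.** The SAP states no figure on this point, so there is none to reproduce. Three checks follow.

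**1. Does the added term make the model complicated?**

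Inputs from Section 7.1.5.1: 13 visits (Week 4 to Week 52, every 4 weeks) and an unstructured covariance.

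- Fixed effects now: 1 intercept + 1 baseline + 1 treatment + 12 visit + 12 treatment-by-visit + 12 baseline-by-visit = 39.
- Covariance parameters: 13 × 14 / 2 = 91.
- With prior ESA use as a main effect: 39 + 1 = 40.
- With its visit interaction as well: 40 + 12 = 52.

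The treatment difference in Section 7.1.5.1 contains only treatment and treatment-by-visit terms, averaged over Weeks 40, 44, 48 and 52. ESA-use terms cancel between arms, so the contrast is written and read as before.

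**2. Size of the conservatism, by formula**

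Let R² be the share of residual variance that ESA use explains. The range 2% to 10% is an assumption; the SAP gives no value.

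- Standard error too large by 1/√(1 − R²) − 1
- Actual one-sided level = 1 − Φ(1.96/√(1 − R²))

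| R² | SE too large by | Actual level (nominal 2.5%) |
|---|---|---|
| 2% | 1.0% | 2.4% |
| 5% | 2.6% | 2.2% |
| 10% | 5.4% | 1.9% |

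**3. Size by simulation**

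Inputs from the SAP: 286 subjects, 1:1 allocation, a true difference at the margin of −1.0 g/dL, a one-sided test at 0.025, and four strata with the Hgb cut nested in ESA use ("Stratum code=1: ESA non-user, Baseline Hgb <= 9.5, 2: ESA non-user, Baseline Hgb > 9.5"; 11.0 g/dL for users). Assumed: blocks of 4, residual SD 0.8 g/dL, 50% users, baseline slope 0.2, baseline Hgb about 11.0 (users) and 9.8 (non-users), and an ESA-use effect d on the Week 40-52 mean. The analysis was ANCOVA on that mean, which with complete data matches the MMRM with visit interactions and unstructured covariance. There were 6,000 runs per setting; the Monte Carlo error of the level is about 0.002.

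| d (g/dL) | SE, omitted | SE, included | Level, omitted | Level, included |
|---|---|---|---|---|
| 0 | 0.0945 | 0.0945 | 0.028 | 0.028 |
| 0.3 | 0.0954 | 0.0946 | 0.023 | 0.024 |
| 0.5 | 0.0970 | 0.0945 | 0.023 | 0.023 |
| 0.8 | 0.1009 | 0.0947 | 0.022 | 0.028 |
| 1.0 | 0.1042 | 0.0946 | 0.018 | 0.026 |

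The mean estimate stayed between −1.001 and −0.997 throughout, so there was no bias. At d = 1.0 the reported SE is 0.1042/0.0946 = 1.10 times the adjusted one. The lower confidence limit then moves by 1.96 × (0.1042 − 0.0946) = 0.019 g/dL, against a margin of 1.0 g/dL. Withdrawal was not simulated.

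**The case against.** The case for leaving the plan alone has four parts.

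**The harm is small and in the safe direction.** This stands. A shift of about 0.02 g/dL or less alters the conclusion only if the result lies that close to the margin. Both arms are also titrated towards a target range, so the effect of prior ESA use by Weeks 40-52 may lie at the low end of the assumed range.

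**Much is already covered.** This stands in part. The MMRM is repeated on ITT within users and within non-users, where everything is conditional on ESA use, and that table is among the headline results (Section 15.10.3). It yields two separate differences, however, and a subgroup that fails to converge is not displayed. The ANCOVA differs from the primary analysis in model, population and covariate at once, so a discrepancy could not be traced to ESA use. The tipping-point analysis does test departures from missing at random, but its imputation model is also without ESA use (Section 7.1.6.3).

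**Interpretation would change a little.** True for the arm means, not for the difference. The ANCOVA weights users and non-users one half each in its LS means. ITT takes only users from Cohort 1, so equal weights need not describe that sample. Observed-margin weights deal with this.

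**The choice is disclosed and pre-specified.** True, and it rules out any suggestion of concealment. It does not make the stated reason sound.

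A reader might infer that the omission could produce a false claim of non-inferiority, or that the primary estimate is biased. The documents do not support either. With complete data and stratified randomization the estimate is unbiased and the level does not rise. Bias would require both withdrawal and later Hgb to depend on ESA use beyond what baseline and observed Hgb capture; the SAP gives no information on that.

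**Conclusion.** The point holds as a matter of avoidable inefficiency and inconsistency, not of validity. The primary MMRM omits a stratum that the SAP itself calls important for Hgb and uses in its other two models, and the complexity argument fails because the other stratum is already handled with a visit interaction.

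With complete data the consequence is a standard error 1.0% to 5.4% too large and a one-sided level of 2.4% to 1.9%, on an assumed R² of 2% to 10%. In the simulation the overstatement runs from 0 to about 10% for an assumed ESA effect of 0 to 1.0 g/dL, with a residual SD of 0.8 g/dL. These sizes rest on the assumptions listed, not on SAP figures. The missing-at-random assumption is unconditioned on ESA use; whether that causes any bias, and how much, is unknown. The change is worth making because it costs little, not because the non-inferiority conclusion is at risk.

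**What to change.** - In Sections 5.4.1 and 7.1.5.1, add two-level prior ESA use (user/non-user) and its visit interaction as fixed effects in the primary MMRM. Use the two-level factor, not the four-level stratum code, which also contains baseline Hgb.
- In Section 7.1.6.3, add the same factor as a covariate in the imputation model.
- Compute arm LS means and Hgb curves with observed-margin weights, so that they still describe the ITT sample.
- Keep the present model as a sensitivity analysis and list the change in Table 1.
- Do not add cohort: nothing in the SAP justifies it, and within ITT Cohort 1 contains only ESA users, so cohort is partly confounded with ESA use.

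If the primary model can no longer be changed, pre-specify the ESA-adjusted MMRM on ITT as a sensitivity analysis.

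The cost is SAP wording, 13 fixed-effect parameters and one more fit. As the trial is open-label, the change to the primary model should be documented and dated before database release.

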5.4.2. Examination of Subgroups

The list of subgroups may be used in descriptive summaries and statistical analyses.

Subgroup	Categories
Prior ESA Use ^[1]	Non-user, User
Baseline Hgb (g/dL) ^{[1][2]}	ESA non-users: <=9.5, >9.5 ESA users: <11.0, >=11.0
Age (year)	< 65, >=65
Sex	Female, Male
Prior ESA Dose (IU/week)	<4,500, >=4,500 ^{[3][4]}
Prior ESA Type	Epoetin, Epoetin beta pegol, Darbepoetin alfa
ERI ^[3]	< median, >= median
Baseline Iron Use ^[5]	Yes, No

Subgroup	Categories
Baseline Weight (kg)	< 55, >=55
Baseline BMI (kg/m ²)	<20, >=20
History of Diabetes ^[6]	Yes, No
Dialysis ^[7]	ND subjects, PD subjects
CKD Stage ^[8]	Stage 3 (30=<eGFR<60), Stage 4 (15=<eGFR<30), Stage 5 (eGFR<15)

NOTES:

- BMI = Body Mass Index
 - See Section 15.6.1 for the subgroup derivations
- [1] Stratum code will be used to determine category. Stratum code=1: ESA non-user, Baseline Hgb <= 9.5, 2: ESA non-user, Baseline Hgb > 9.5, 3: ESA user, Baseline Hgb < 11.0, 4: ESA user, Baseline Hgb >= 11.0.
- [2] Hemocue Hgb at Day 1 will be used for categorization.
- [3] Additional thresholds might be added in order to divide the population equally as appropriate.
- [4] Standardized dose on epoetin i.v. (IU/week) will be used for subgroup.
- [5] Subjects who used ferric citrate (trade name: Riona) will also be included in Baseline Iron Use group. This category will be used just for iron analyses. See Section 15.6.3.
- [6] Past or current history of diabetes
- [7] This subgroup will be used for study population analyses and safety analyses.
- [8] CKD Stage will be determined by eGFR (mL/min/1.73m²) at a screening visit

For prior ESA use, the subgroup of non-users in PD subjects is small. Therefore endpoints summarized for PD subjects (i.e. Safety or Efficacy PD population) by prior ESA use will also be listed for the ESA non-users in PD subjects.

5.5. Multiple Comparisons and Multiplicity

Adjustment for multiplicity will be applied to maintain an overall type I error rate of 2.5% (one-sided, change from define in the protocol, see Section 2.1). After a preliminary assessment, the primary endpoint will be evaluated to demonstrate the non-inferiority at a one-sided significance level of 2.5%. Only when the primary endpoint achieves non-inferiority, statistical testing will progress to the principal secondary endpoint with a focus on superiority. Since the process will follow step-down manner, a multiplicity adjustment for one-sided significance level of 2.5% will not be needed according to a closed test procedure.

Other secondary endpoints, which will be evaluated on a complementary or exploratory basis, will be compared at a two-sided significance level of 5% without multiplicity adjustment.

Since Cohort 2 is a single-arm cohort, no testing will be performed to evaluate the efficacy in PD subjects.

5.6. Other Considerations for Data Analyses and Data Handling Conventions

Other considerations for data analyses and data handling conventions are outlined in the appendices:

Section	Component
15.3	Appendix 3: Assessment Windows
15.4	Appendix 4: Study Phases and Treatment Emergent Adverse Events
15.5	Appendix 5: Data Display Standards & Handling Conventions
15.6	Appendix 6: Derived and Transformed Data
15.7	Appendix 7: Reporting Standards for Missing Data
15.8	Appendix 8: Values of Potential Clinical Importance

6. STUDY POPULATION ANALYSES

6.1. Overview of Planned Study Population Analyses

The study population analyses will be based on the specified population. For the populations including both ND and PD subjects (All Screening, Enrolled, Randomized, Safety), the summaries will be provided by dialysis (ND and PD separately) unless otherwise specified.

Study population analyses including analyses of subject's disposition, protocol deviations, population analysed, demographic and baseline characteristics, medical conditions and concomitant medications, and exposure and treatment compliance will be based on GSK Core Data Standards. Analysis of dialysis will also be included. Details of the planned displays are presented in [Appendix 10: List of Data Displays](#).

Endpoint / Parameter / Display Type	Population	Data Displays Generated		
		Table	Figure	Listing
Subject's Disposition				
Subject Status and Reason for Study Withdrawal	Randomized	Y		
Reasons for Study Withdrawal	Randomized			Y
Treatment Status and Reasons for Discontinuation of Study Treatment	Safety	Y		Y
Screening Status and Reasons for Screen Failure	All Screening	Y		Y
Subjects Enrolled by Country and Site ID	Enrolled	Y		
Planned and Actual Treatments	Safety			Y
Protocol Deviations				
Important Protocol Deviations	Randomized	Y		Y
Subjects with Inclusion/Exclusion Criteria Deviations	Randomized	Y		Y
Populations Analyzed				
Study Populations	Randomized	Y		
Exclusions from the Per Protocol Population	mITT	Y		Y
Subjects Excluded from Any Population	Randomized			Y
Composition of Randomized Population	Randomized	Y		
Demographic and Baseline Characteristics				
Demographic Characteristics	ITT/Safety/Efficacy ND/Efficacy PD	Y		Y
Demographic Characteristics by Prior ESA Use	ITT/Safety/Efficacy PD	Y		
Demographic Characteristics by Cohort	Efficacy ND	Y		
Other Baseline Characteristics ^[1]	Safety			Y
Prior ESA	ITT/Safety/Efficacy PD	Y		Y
Age Ranges	Enrolled	Y		
Race and Racial Combinations	Safety	Y		Y ^[1]
Family History for CV Risk Factors	Safety	Y		Y

Endpoint / Parameter / Display Type	Population	Data Displays Generated		
		Table	Figure	Listing
Substance Use (History of Tobacco Use, Alcohol Intake)	Safety	Y		Y
Dialysis				
Subjects with Dialysis Initiation during the Study Period	Safety			Y
Subjects with Peritoneal Dialysis at Baseline	Safety			Y
Subjects with Vascular Therapeutic Procedures during the Study Period	Safety			Y
Medical Conditions and Concomitant Medications				
Current/Past Medical Conditions	Safety	Y		Y
Concomitant Medications ^[2]	Safety	Y		Y
Other Concomitant Medications (ESA, iron, and anti-hypertensive medication)	Safety	Y ^[3]		Y
Blood products and blood supportive care products	Safety	Y		Y
Exposure and Treatment Compliance				
Exposure to Study Treatment	Safety	Y		Y
Treatment Compliance	Safety	Y		Y ^[4]

NOTES :

- Y = Yes display generated.

[1] As a separate listing, include prior ESA type, standardized prior ESA dose, ERI, iron use, diabetes, and CKD stage.

[2] Listing of race.

[3] Concomitant medications in pre-therapy, on-therapy, and post-therapy period will be summarized separately.

[4] On-therapy ESA, on-therapy iron, and on-therapy anti-hypertensive medications will be provided. .

[5] For Daprodustat in cohort 3, compliances up to Week 2 and Week 2 to 4 will be including in the listing

